### Confidentiality and Privacy:

The use of questionnaires, interviews, and collection of personal medical information poses a risk to confidentiality and privacy and may cause embarrassment.

### **Adequacy of Protection Against Risks**

#### Informed Consent and Assent:

Recruitment for participation in the study will occur following IRB approval. Study staff will complete a training to standardize the recruitment and consenting procedures. The consenting process is part of the initial study visit, which will take place remotely over Zoom. Volunteers will meet remotely with a member of the research team to a) have the study explained in detail; b) discuss their reasons and motivation for wanting to participate to determine whether they are realistic; c) discuss any practical problems (e.g., scheduling conflicts, vacations) that could interfere with participation; d) have their questions answered; and e) demonstrate their ability to provide informed consent by describing their understanding of the major study goals and what is expected of them if they choose to participate.

Participants are provided with a digital signed copy of the consent form and a signed copy is maintained in the study chart for each participant. HIPAA authorization is included in the consent form. The PI, [name], will have the responsibility of ensuring that research personnel are prepared to convey information to participants specific to the study protocol. The individual is informed of the purpose of the study, potential medical and social risks of participation, their right to withdraw at any time, and compensation. If willing to participate, the volunteer and a study team member will sign the document.

#### Protections Against Risk:

The inclusion/exclusion criteria are designed to assure that participants at highest risk for adverse events (AEs) are excluded while preserving study generalizability. In addition, the specific measures to decrease risks on the study procedures are detailed below.

#### Confidentiality and Privacy:

Risks will be minimized by not including personal identifying information on the forms, when possible, and by conducting remote interviews and collection of personal information in a private setting. Reminder text messages will make no mention of HIV. All data will be collected using unique patient identification codes. All laboratory specimens, evaluation forms, reports, and other records will be identified by a coded number to maintain participant confidentiality. All records will be stored in a locked file cabinet. Study data will be collected and managed using REDCap. REDCap is a secure web application designed to support data capture for research studies, providing user-friendly web-based case report forms, real-time data entry validation (e.g., for data types and range checks), audit trails, and a de-identified data export mechanism to common statistical packages (SPSS, SAS, Stata, R/S-Plus). REDCap data collection projects rely on a thorough study-specific data dictionary defined in an iterative self-documenting process by all members of the research team. This iterative development and testing process results in a well-planned data collection strategy for individual studies. REDCap also includes a powerful tool for building and managing online surveys. The research team can create and design surveys in a web browser and engage potential respondents using a variety of notification methods. REDCap is flexible enough to be used for a variety of types of research and provides an intuitive user interface for database and survey design and data entry. Lastly, clinical information will not be released without written permission of the participant, except as necessary for monitoring by the IRB or the

National Institutes of Health (NIH).

**Unexpected and Serious Adverse Event Reporting:**

The study team will regularly review the data to ensure the integrity and safety of the participants. The research coordinator will report serious adverse events (SAEs) that are unexpected and study-related immediately to a study physician who will convey this information to the study team, IRB, and NIH. All AEs and SAEs will be captured, reports will be completed, and information will be entered into the study database. A safety report will detail all serious and unexpected AEs or other unanticipated problems that involve risk to study participants or others and whether these appeared to be related to the study-based interventions or research assessment protocols. If the study team, CUIMC, IRB, or NIH has concerns regarding SAEs, a copy of the safety summary will be filed with the IRB. Actions taken by CUIMC IRB offices in response to AE concerns will be reported to the NIH. All AEs will be reviewed every six months, or sooner, with the designated safety officer.

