**Table 1. Components of CHAMPS Pilot delivered over the 3-month intervention period**

10 sessions with the CHW	Detailed in Table 3 below
CleverCap	Participants and CHW will be able to track ART adherence.
WiseApp	
 
CHW will be able to deliver sessions to the study participants through the WiseApp.
 
Participants will be able to self-manage their health through the content described in Table 2.
 
Participants and CHW can securely chat with one another.
 

**Intervention Training and Support.** The CHW will be trained on the intervention: content of each session, MI, strengths-based case management, ARTAS, HIV and substance

use, and safety in the field. The CHW will also be trained on use of the WiseApp and CleverCap assuring all study participants and CHW are able to successfully use the mHealth technology. Training for the CHW will also be provided on: human subjects research protection, financial conflict of interest, HIPAA, and data privacy and security. The CHW will engage in supportive strengths-based case management and MI with the study participant. Intervention visits (~ten over a 3-month period) will help participants access primary medical care by acknowledging and addressing barriers to care. Participants will participate in CHW sessions via the App. This will help participants overcome many of the challenges to participating in-person, which has been a frequent barrier due to COVID-19.

The WiseApp offers the following functionality listed in Table 2, and the CleverCap is linked to the WiseApp. The CleverCap fits on standard pill bottles, dispenses only the prescribed amount of medication, keeps track of medications dispensed, and communicates wirelessly with mobile devices. Participants are then able to self-monitor their medications, and the CHW will also be able to track study participants' adherence to their ART medication in real time. Participants receive reminders through the WiseApp when they have not taken their medication on time and receive encouraging messages (e.g., Great job! You've met your goal for not forgetting your meds) when they have taken their medication.

Communication via the App will enhance the relationship between the CHW and the study participant.

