### Standard of Care (Control Arm)

The control condition includes standard health services (e.g., mental health services, case management, referral to clinical care) and a brief adherence educational session. The standard educational session consists of a review of medications and recommended dosing (i.e., to understand regimen), adherence expectations, toxicity expectations, and medication misperceptions. During the educational session, participants can ask questions and receive answers to reinforce their current ART regimen. All participants receive referrals to mental health, drug/alcohol treatment, and/or other HIV services as necessary. In summary, standard of care is comprehensive (far more extensive than standard of care for the general non-HIV infected population) and follows the Department of Health and Human Services HIV guidelines. Participants are also provided with mental health and psychosocial support services.

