### Randomization

Using the randomization approach described below, there will be random or minimally biased assignment of subjects to study arms. Randomization will be achieved through a blocked design utilizing permuted blocks of random sizes. The design ensures equal representation of treatment assignment across groups and protects the study team and investigators from easily anticipating treatment allocation. Randomization to CHAMPS Pilot or standard of care is 1:1. Participants will be randomized using computer-generated random numbers at baseline. The randomization database will be stored on a password protected computer at Columbia University and will only be accessible to PI [name]. Following completion of the informed consent and baseline assessment, participants will be randomly assigned to one of two trial arms in REDCap.

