### Procedures

All study visits will occur remotely via Zoom. Staff members will collect digital informed consent prior to enrolling into the study trial (See Protection of Human Subjects). The informed consent form provides details of the study procedures, risks, benefits, site contact information, and the nature of confidentiality and voluntary participation. The consent process also covers information on the study and compensation for time.

Participants in both the intervention and control arms will complete remote visits at the baseline and 3-month follow-up. Following the completion of the baseline study instruments, study participants in the CHAMPS Pilot intervention arm will be mailed a CleverCap™ Lite dispenser and trained on how to use it; they will also be trained by study team members on how to use the different features of the Wise App and receive medication reminders. Upon assignment to the intervention arm, a CHW is assigned to and meets with the participant as soon as possible, generally on the same day but no more than five business days. The CHW will deliver the interventions outline in Table 3 remotely throughout the course of the study. Participants will also be provided the opportunity to complete a follow-up interview at their follow-up visit. Follow-up interviews will be recorded via Zoom and will be semi-structured. Study staff members will take field notes and interview recordings will be transcribed prior to analysis.

Dried Blood Spot (DBS) kits will be used to measure participant viral load. DBS kits will be shipped to participants, allowing them to collect their sample in their home or other secure environment. Instructions will be included with the kit, including information about how to collect the dried blood spot and how to mail the sample back to the research team. Participants will be instructed to call research staff to confirm they have

received the kit, have collected the sample, and have mailed the sample back, as well as if they have any questions.

Participants will be texted appointment reminders for study visits. Hard to reach participants will also be sent scheduling reminders. These reminders will be sent via Qualtrics, REDCap and/or encrypted e-mails from the study's secure CUMC e-mail address.

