**Table 4. Measures and Schedule of Events**

	Screening	Baseline	3 mos
Sociodemographic:(e.g., age, race/ethnicity, education, housing)		X	
Primary Outcome Measures			
Viral Load through dried blood spot kit	X		X
Secondary Outcome Measures			
ART adherence (SRSI)  and the CleverCap (intervention group only)	X		X
Additional Outcome Measures			
Quality of Life (PROMIS-29) 		X	X
HIV Symptom Index 		X	X
Engagement in HIV Care 		X	X
Mediators			
The HIV Medication Taking Self-Efficacy Scale		X	X
Motivation and outcome expectancies of ART adherence are assessed as three separate dimensions: attitudes, norms, and behavioral intentions to adhere to ART medication 		X	X
Self-regulation skills, which include self-monitoring, goal-setting, and enlistment of self-incentives/plans 		X	X
HIV-regulated Stigma 		X	X
Moderators			
Alcohol, Smoking & Substance Involvement Screening Test (ASSIST) 		X	X
Depression and Anxiety (Beck Symptom Inventory) 		X	X

and has ceiling effects. Finally, the electronic pill box is limited to data collected from the intervention group. While this is a limitation, providing the electronic pillbox to the standard of care (control group) is likely to bias our intervention effects since this pillbox will, in fact, have intervention effects as we have found from our preliminary findings from our WiseApp trial. We closely considered each of these limitations and have, therefore, decided that this three-pronged (i.e., viral load, self-report, and electronic pillbox) approach which will provide the most rigorous approach to measuring our primary and secondary outcomes of viral suppression and ART adherence.

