**Study Procedures, Materials, and Potential Risks**

**Study Procedures and Materials:**

All materials for the proposed study obtained from the participants will be in the form of specimens, EMR information, and data. Principal Investigator (PI), [name], will be responsible for ensuring all information is collected according to the study protocol. Information used to identify potentially eligible participants will be obtained using the NYP-CHP EMR systems. We will also use patient-reported data obtained after consent. Trained and certified professional staff will obtain all data according to detailed study protocols. Data will be collected directly from study participants and their respective EMR and used specifically for research purposes.

The following human subjects-related data elements will be collected for this study with the source(s) of information noted:

- Participant demographic and clinical characteristics including age, sex, gender, race/ethnicity, employment status, and ART adherence (self-report)
- Clinical diagnoses, clinical HIV lab values (viral load), medication history, comorbid health conditions, and primary care visit data (electronic medical records)
- Laboratory measured values of viral load (dried blood spot collection)
- Notes from the CHW encounters with the study participants
- Usage data captured through the WiseApp and the electronic pill bottles (CleverCap)

Our study team is extremely prudent in keeping subject data secure and confidential. All laboratory specimens, evaluation forms, reports, and other records will be identified by a unique coded number to maintain participant confidentiality. The material, records, and data obtained through participation in the study will be specific for research purposes. Existing health records may be used with the permission of the participants. Materials will be obtained by trained staff. Data will be stored using REDCap (Research Electronic Data Capture). All laboratory specimens will be identified *only* by the identification number. The code linking the participant identification number to subject identifying information (name, address, etc.) is maintained through REDCap, and only authorized site personnel have access to the code. Limited individually identifiable private information is collected that is essential for processing participant payments and for analysis purposes.

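### All adverse events are to be captured, but no ascertainment method is described and contact differs sharply by arm, so events are likely to be under-recorded in controls

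*Combined protocol and SAP*

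**What the plan says.** The section on unexpected and serious adverse event reporting states that "All AEs and SAEs will be captured, reports will be completed, and information will be entered into the study database". It also promises a safety report on serious and unexpected events, covering their relation to the interventions or to the research assessments, and a review of all AEs with a safety officer at least every six months. It names no form, question, visit or recall period.

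On contact, Procedures says "Participants in both the intervention and control arms will complete remote visits at the baseline and 3-month follow-up". Randomization comes after baseline: "Following completion of the informed consent and baseline assessment, participants will be randomly assigned to one of two trial arms in REDCap". The Intervention Training and Support text after Table 1 adds, for the intervention arm only, "Intervention visits (~ten over a 3-month period) will help participants access primary medical care". That arm also has one-to-one chat in the app (Table 2), and the data elements under Study Procedures and Materials include "Notes from the CHW encounters with the study participants". The Standard of Care section gives controls "a brief adherence educational session", which is undated and does not appear in Table 4.

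Table 4, "Measures and Schedule of Events", has columns for screening, baseline and 3 months and no AE row. The five data elements under Study Procedures and Materials include no AE item. Data Analysis allows for 20% attrition between randomization and 3 months.

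**The concern.** Complete capture is a stated property of the plan, and no described procedure delivers it. Where no one is told to ask, what gets recorded depends largely on how often a participant is in touch with study staff, and here that frequency is set by the assigned arm. Equal true event rates could then appear as more events under CHAMPS Pilot and few under standard of care.

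What is at stake is the AE listing, the safety officer's review, judgements of relatedness, and any by-arm AE summary published or used in planning a later trial. The viral suppression outcome is not touched.

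**Working it through.** The documents give no AE rate and no contact count, so there is no figure of the plan's to reproduce. The check is a count followed by an illustration.

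**Count of scheduled contacts**
- Intervention: 10 CHW sessions + baseline + 3 months = 12. Baseline precedes assignment, so 10 + 1 = 11 follow randomization.
- Control: baseline + 3 months = 2, or 3 with the educational session. After randomization: 1, or 2 if that session is counted.
- Calls about dried blood spot (DBS) kits come on top in both arms, and chat comes on top in the intervention arm.
- With 40 participants allocated 1:1 there are about 20 per arm. If attrition is equal by arm, 0.20 × 20 = 4 controls miss their only scheduled assessment after randomization.

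**Illustrative capture model.** These assumptions are not in the documents:
- AE onset is uniform over 3 months.
- The ten sessions are evenly spaced and all attended.
- Each contact after onset brings the event into the AE record with probability p, the same for a CHW session and a staff visit.
- The 3-month visit is attended by a fraction r.
- The educational session comes too early to detect events.

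With k sessions remaining after onset (k = 0 to 10, equally likely):
- Intervention share = mean over k of 1 − (1−p)^k × (1 − p·r)
- Control share = p·r

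Example with p = 0.5 and r = 0.8: the mean of 0.5^k over k = 0 to 10 is 1.999/11 = 0.182. The intervention share is 1 − 0.182 × 0.6 = 0.891, the control share is 0.40, and the ratio is 2.23.

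| p | r = 1: intervention v control (ratio) | r = 0.8: intervention v control (ratio) |
|---|---|---|
| 0.2 | 67% v 20% (3.3) | 65% v 16% (4.1) |
| 0.5 | 91% v 50% (1.8) | 89% v 40% (2.2) |
| 0.8 | 98% v 80% (1.2) | 96% v 64% (1.5) |
| 1.0 | 100% v 100% (1.0) | 98% v 80% (1.2) |

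With an assumed 6 true events per arm, the p = 0.5, r = 0.8 case records 6 × 0.891 = 5.3 against 6 × 0.40 = 2.4.

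**Effect of a common source.** Suppose a review of electronic medical records (EMR) independently finds a fraction e of events in both arms. Each share s becomes 1 − (1−s)(1−e). For p = 0.5 and r = 0.8:
- e = 0.3: 92% v 58%, ratio 1.6
- e = 0.6: 96% v 76%, ratio 1.3
- e = 0.9: 99% v 94%, ratio 1.05

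**Does a common question at 3 months suffice?** The p = 1, r = 0.8 row shows that it does not if CHW-detected events are pooled: 98% v 80%. If a by-arm statement uses only the commonly elicited events, both arms stand at 80% when attrition is equal.

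**The case against.** The strongest reply is that a reader might infer that events can enter the record only when a participant volunteers them. The documents do not support that. EMR diagnoses and visit data are listed without restriction to one arm, and consent to record access is an inclusion criterion. Both arms complete the HIV Symptom Index, PROMIS-29 and a depression and anxiety inventory at baseline and 3 months. Participants in both arms are told to call staff about DBS kits. This stands, and it lowers the likely imbalance. But none of these is named as an AE source. The only EMR system named is one used to identify potential participants, while recruitment is national. Records are also unlikely to show most of the named risks: discomfort with questions, breaches of confidentiality and problems with blood spot collection.

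Neither list is exhaustive, either. Table 4 omits the EMR missed-visit measure, and the data elements omit several Table 4 scales. Absence from both lists therefore does not prove that AEs go uncollected. What can be said is that no ascertainment method is described.

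The study is also small, lasts three months, is classed as minimal risk and plans no between-arm AE comparison. That limits the consequences but does not meet the commitment to capture every event. Finally, the model assumes that all CHW sessions are attended and that what CHWs hear reaches the AE record. The background section reports difficulty attending CHW sessions in the predecessor trial, and the plan does not describe a route from CHW to AE record.

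**Conclusion.** The gap is real. All AEs are to be captured, no method is given, and scheduled contacts after randomization are about 11 against 1 or 2. AEs are likely to be under-recorded in controls, and a by-arm listing produced under the plan as written would not be comparable.

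The size cannot be determined from the documents. The illustrative ratio runs from 1.0 to 4.1 and rests wholly on the assumed reporting probability, attendance and EMR yield. A reader might go further and conclude that control counts are certain to be incomplete and biased, or that a planned safety comparison between arms is invalid. The documents establish neither: the bias is an inference about reporting behavior, and no such comparison is planned. The point merits a change because the remedy is cheap and makes a stated safety commitment deliverable.

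**What to change.** - Add an AE row to Table 4 and an AE item to the data elements under Study Procedures and Materials.
- At 3 months, ask both arms the same short fixed AE and social-harm questions with the same recall period. Include unwanted disclosure of HIV status, distress and blood spot problems.
- Put the same questions to non-attenders through the reminder contacts already planned in Procedures.
- State whether the EMR is an AE source and, if so, that it is searched in the same way in both arms.
- Record the source of each event. List CHW-detected events separately, and base any by-arm statement only on events elicited by the common questions.

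The cost is one short REDCap form at a visit both arms already attend, a few minutes per participant and a sentence on reporting. The downside is that CHW-reported events are left out of any by-arm comparison, though they are still listed and reviewed.

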**Vulnerable Subjects:**

Economically and/or educationally disadvantaged persons will be enrolled. While this group is considered a vulnerable population, the study team has considerable experience enrolling these participants. As these groups carry the burden of the majority of HIV incidence and demonstrate considerable challenges with achieving optimal HIV health outcomes, it is important that they are not excluded from participation in this study. Additionally, our study will analyze the potential impact of the intervention(s) on racial and ethnic groups, perhaps providing new information on the disproportionate impact of HIV felt by these populations.

The study will be conducted according to Good Clinical Practice (GCP) guidelines, the U.S. Code of Federal Regulations (CFR) Title 21 CFR (Part 50 – Protection of Human Subjects and Part 56 – Institutional Review Boards) and the Declaration of Helsinki. This protocol will be submitted to the IRB for approval. The informed consent of each subject will be obtained in accordance with 21 CFR Part 50 and the Declaration of Helsinki before protocol-specified procedures are carried out.

A study member will obtain the participant's digital informed consent prior to any study-related procedures. Consent will be documented by the dated signature of the subject. The signature confirms that the consent is based on information that has been understood. Each subject's signed informed consent form will be kept in secure files by the investigators for possible inspection by regulatory authorities.

